4.0 Supportive Care

Study investigators and support staff will provide further consultation to participants by in-person visits, phone or electronic communication as needed to address participant concerns regarding study therapy or imaging evaluation.

5.0 Data Collection and Evaluation

5.1 Data Collection

Standard forms for patient history, labs, imaging results.

Vital status will be recorded on a case report form. Complete records must be maintained on each patient, which will consist of the hospital chart with any supplementary information obtained from patient, outside laboratories, progress notes, reports, consults, or tests.

> The relational database storing the entire information set will be based on coded identification. The confidentiality and security of the data files in the computer will be maintained by ensuring password protection on all computer accounts. Protection against loss of data is essential to our data management. Quality control procedures will also include:

1) Assurance or the prevention of possible errors;

2) Assessment, or the detection of errors after they have occurred and;

3) Feedback, or the correction of system failures which originated the error and is necessary to avoid errors in the future. Detailed checklists are used for data collection and trial procedures.

Any protected patient information will be stored on a password protected secure database at NIH. Any information will be deidentified by study ID # and cleaned of PHI.

5.2 Response Criteria

A. Lipid targets will be used as response criteria study.

5.3 Toxicity Criteria

Table: Safety Parameters to be monitored during the study

Safety	Measure	Method	Concern	Discontinuation	Discont.
issues					Freq.
Liver	ALT, AST	Standard	2 x	3 x normal	2%
Function			normal		

Liver	Alk.	Standard	2 x	3 x normal	<1%
Function	Phosphatase		normal		
Muscle	CK	Standard	3 x	>1000 U/L	<1%
Injury			normal		
Hepatitis	Symptoms/LFTs	History	LFT	Clin. Diagn.	<1%
		-	elev.		

6.0 Statistical Section

Data from the recently concluded NIA Plaque Study, a randomized double-blind trial of the effect of niacin vs. placebo on MRI plaque volumes were collected on 145 subjects at baseline, and at 18-month follow-up. For the primary endpoint in the proposed study, carotid wall volume, the standard deviation of the differences between 18 months and baseline was 125 mm³, combining data from both the left and right arteries. The baseline mean for the entire group was 300.0. Since the proposed study has a longer duration (24 months) than the NIA Plague Study, and since we have the benefit of improvements in MRI technology, we anticipate a larger effect size than was seen in the NIA Plague Study. The sample size calculations were based on finding a 40% decrease in plaque volume in the image-guided arm compared to a 20% decrease in the conventional treatment arm at 24 months using a two-sample t-test. The table below shows the power to detect this difference at the 5% level of significance, assuming 80 subjects in each group. These power calculations were based on comparing the change from baseline at a single time point. However, the primary analysis will employ a mixed model, which will include multiple observations per patient. Therefore, 80 patients in each group will certainly provide adequate power. As discussed below we assume that the attrition rate will be 0.20 at the 24-month follow-up. Thus, recruiting 200 study participants will be sufficient for this study. These calculations were based on the optimal allocation of equal numbers to the two arms. However a 3/1 ratio of image-guided to conventional therapy did not meaningfully reduce the power.

		Decrease in Plaque Volume (Control Art		
Decrease in		15%	20%	25%
plaque volume	35%	0.85	0.62	0.33
(Image guided	40%	0.96	0.85	0.62
arm)	45%	0.99	0.96	0.85

Power of a two-sample t test to detect the indicated difference in change from baseline at 24 months

For the secondary end-point of this study, the task is to test the null hypothesis that the hazard rate, which is assumed to be constant across all study months, is identical in the two groups (image guided vs.

traditional risk-factor based care). This hypothesis will be tested in a study in which subjects are entered and then followed until either (a) the terminal event occurs, or (b) they drop out of the study, or (c) the study ends and the patient is censored while still being actively followed. The study design calls for an accrual period of 50 months and a follow-up period of 24 months. Computation of power for this analysis is based on a hazard ratio of 0.50. Specifically, it assumes hazard rates of 1.00 for the standard care group, versus 0.50 for the image guided group. Since the hazard rate is constant across months, this is equivalent to median survival times of 0.69 years for the standard treatment versus 1.39 years for the image guided intervention group.

The power analysis for the secondary outcome (clinical events) was based on the paper by Brown et al.²⁴ This paper reported mortality rates at 30 months in two treatment groups (2/48 = 0.042 and 3/46 = 0.065) and a control (10/52 = 0.192). We used these rates, as well as the combination for the two treatment groups (5/94 = 0.053). The calculation of power was based on the log-rank test⁽²⁵⁾ assuming a 24 month study. Using a twosided test at the 5% level of significance, we obtained the following results.

 			
Treatment	0.042	0.053	0.065
Mortality Rate			
Sample			
Size/group			
50	0.57	0.47	0.38
80	0.82	0.71	0.59
100	0.91	0.82	0.70

Power of the log-rank to detect the indicated difference from control

We assume that the attrition rate will be 0.20 in the 24-month follow-up. Thus, recruiting 200 study participants with 160 anticipated to complete 24 months of follow-up will be sufficient for this study.

Data Analysis:

1. The intent-to-treat and missing data:

The intent-to-treat (ITT) approach will be used for the primary analysis. According to this generally recommended approach, comparisons are made according to randomized treatment assignment, regardless of any changes in dose, schedule or treatment arm. In an ITT analysis, all randomized study participants are included in their assigned treatment groups, regardless of compliance with the assigned treatment regimen. On the other hand, the weakness of ITT is that it assesses the effect of treatment for subjects known not to have used the treatment enough to have any effect. While conventional ITT will be the method used to analyze and report the primary results, in order to derive valid estimates of treatment effect accounting for compliance with therapy, model-based analytical methods will also be employed, and non-ITT analysis will be performed.

In fact, in the present study, we do not foresee noncompliance as a problem since treatment administration is under the control of the study physician rather than the patient. Dropout, however, is always a potential problem. In this study we have assumed a dropout rate of 20%, since we anticipate a lower dropout rate than the 25% in the previous trial. This is because we are using three scans over two years rather than four over 18 months as in the previous study, and many of the previous dropouts were related to MRI anxiety. Thus we do not anticipate problems with differential dropout. In addition, approximately one-third of the dropouts in the previous study were due to problems with niacin flushing, which again will not be a problem in the present study.

2. Multiple outcome measures:

In this clinical trial, we will evaluate multiple outcome measures: changes in plaque architecture and composition measured by MRI, and time to events, including the incidence of cardiovascular and cerebrovascular outcomes and disease-specific death. The following approaches to evaluate multiple outcome measures will be implemented: (i) defining a primary outcome measure; (ii) correcting for multiple testing, such as Bonferroni adjustment; (iii) with data on major clinical events, adopting a combined endpoint, such as time to first cardiovascular event or death, whichever occurs first.

3. Data Analysis:

Standard statistical methods⁽²⁴⁾ will be used to describe the demographic characteristics, clinical manifestations and basic summary statistics as rates or means (medians). Confidence intervals will also be computed. If necessary, permutation methods⁽²⁶⁾ will be employed.

For Hypotheses 1, 2, and 4:

Linear mixed (random-effects) models⁽²⁷⁾ will be used to study differential changes over time in plaque size and composition and drug dosage between the two treatments. Each model will include main effects of time from baseline and treatment, with interactions tested separately. To decide on the correlation structure for these models, variation due to random effects, serial correlation and measurement error will be examined using the variogram. These models will also be used to isolate specific comparisons of outcome variables at specific time points between the two arms. The required assumptions of normally distributed errors and random effects can be checked by an analysis of standardized residuals. which are now available for the mixed model. In the event that the assumptions are not satisfied, usually because of skewed error distributions, data transformations from the Box-Cox power family will be considered. The most commonly used member of this family is the logarithmic transformation, which usually corrects a problem with right skewness.

For Hypothesis 3:

For the time-to-event data, both the Kaplan-Meier estimate and the Cox proportional hazards model will be employed. The primary analysis will compare the two treatments using a log-rank test. Secondary analyses will use the Cox model to include adjustment for covariates. A non-parametric proportional hazards model will also be used to explore possible transformations of independent variables in the models⁽²⁸⁾.

For Hypothesis 5, 6, and 7:

Using appropriate parametric and non-parametric tests at and between both the baseline and 6 month time points, a comparison of the presence or absence of atherosclerotic plaque by PET and CT / MRI will be performed. FDG accumulation (with both TBR and SUV_{max}) will be compared across different plaque morphology and compositions defined by MR / CT (for example, presence of a lipid core or calcification). Correlation between imaging findings and changes will be made with age, gender, traditional risk factors (height, weight, hypertension, etc.), absolute values and changes in statin dose, total cholesterol, LDL, HDL, triglycerides and hematological biomarkers markers of inflammation, thrombosis and atheroprotection.

For Hypothesis 8:

Agreement between the two blinded readers of semiquantitative measures of CT angiographic stenosis will be measured using weighted kappa. Quantitative analyses of coronary arterial wall volume, lumen volume and plaque composition will be assessed using the intraclass correlation coefficient (ICC) and Bland-Altman plots.

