1.0 Introduction

1.1 Study Objectives:

The purpose of this study is to evaluate the hypothesis that use of atherosclerosis imaging to set targets for cholesterol lowering therapy will result in greater regression of atherosclerosis than standard therapy.

The primary efficacy endpoint of this study is the wall volume of the internal carotid arteries as measured by magnetic resonance imaging.

Secondary endpoints are

- A. Arterial stenosis and plaque volume measured by coronary MDCTA
- B. Dosage of statin medications required to achieve LDL targets.
- C. Combined incidence of stroke, nonfatal MI, myocardial revascularization, hospitalization for unstable angina or heart failure and death.
- D. FDG plaque uptake within the carotid and coronary arteries.

E. Reproducibility of arterial stenosis and plaque volume measured by MDCTA.

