7.4 Risks/Benefits Analysis

The principal risks to participants are intensive statin therapy, exposure to ionizing radiation as part of the coronary CT angiogram, receipt of iodinated contrast and receipt of gadolinium based contrast. As noted in 7.3, above, large clinical trials have demonstrated low rates of significant adverse events due to statins, few if any of which persist after drug discontinuation. The study population has been specifically selected to be at the lowest risk for ionizing radiation, and the CT protocol carefully tailored to ensure delivery of the lowest possible dosage necessary to generate diagnostic images. The limitation of enrollment to patients with GFR > renders the risk of iodinated and gadolinium based contrast negligible.

The level of risk to the research participants was initially determined to be greater than minimal risk (45 CFR 46 102). As of January 2017, the study status of this protocol changed to "data analysis only" and the level of risk of this study is now minimal.

This research involves the prospect of direct benefit to individual subjects through potential identification of clinically silent atherosclerotic disease and according intensification of statin therapy that would not otherwise be indicated in usual clinical care. This carries the likelihood of significant reduction (16-21% relative risk reduction) of the risk of clinical cardiovascular events.⁴⁷

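### The clinical-event power section states a hazard ratio of 0.50, but its only power table is built on hazard ratios of about 0.20 to 0.32 and a control hazard nearly 12 times lower

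*Combined protocol and SAP*

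**What the plan says.** Section 6.0 gives two bases for one calculation.

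- The first paragraph on the secondary endpoint says "Computation of power for this analysis is based on a hazard ratio of 0.50" and continues: "Specifically, it assumes hazard rates of 1.00 for the standard care group, versus 0.50 for the image guided group". It converts these to median times of 0.69 and 1.39 years, which fixes the hazards as annual.
- The next paragraph takes from a published trial "mortality rates at 30 months in two treatment groups (2/48 = 0.042 and 3/46 = 0.065"), with a control rate of 10/52 = 0.192, and says "We used these rates, as well as the combination for the two treatment groups (5/94 = 0.053"). The method is a two-sided 5% log-rank test over 24 months. The table's columns are headed by these treatment rates, with power of 0.57/0.47/0.38 at 50 per group, 0.82/0.71/0.59 at 80, and 0.91/0.82/0.70 at 100.

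Directly after the table, and allowing for 20% attrition, the plan concludes that "recruiting 200 study participants with 160 anticipated to complete 24 months of follow-up will be sufficient for this study".

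The source rates are described as mortality. The endpoint in section 1.1 is a composite: "Combined incidence of stroke, nonfatal MI, myocardial revascularization, hospitalization for unstable angina or heart failure and death".

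**The concern.** The two paragraphs cannot describe the same calculation. A control hazard of 1.00 per year means that 86% of controls have an event within 24 months. The rates behind the table mean about 16%. The effect sizes differ as well: a halving of hazard in the text, a reduction of roughly 70% to 80% in the table.

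A reader who relies on the hazard-ratio sentence would take 0.82 or 0.91 as the chance of detecting a halving of event risk. The log-rank test is the primary analysis for the third aim, so a non-significant result could be read as evidence against a halving that the trial had little power to detect. The statement that the sample size is sufficient follows the event table and rests on it only in its most favourable column.

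**Working it through.** **Inputs, all from section 6.0.** Stated hazards 1.00 and 0.50 per year. 30-month rates 0.192 (control) and 0.042, 0.053, 0.065 (treatment). 24 months of follow-up, two-sided 5% test, equal arms, 20% attrition, 80 completers per arm.

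**1. The stated medians are internally consistent.** ln 2 / 1.00 = 0.69 years; ln 2 / 0.50 = 1.39 years.

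**2. What the table's rates imply.** Under a constant hazard:
- Control hazard = -ln(1 - 0.192)/2.5 = 0.0853 per year. The 24-month risk is 1 - exp(-2 × 0.0853) = 0.157.
- Ratio to the stated control hazard: 1.00/0.0853 = 11.7. If 0.192 is read as a 24-month rate, the ratio is 9.4.
- Hazard ratio = ln(1 - p)/ln(1 - 0.192) = 0.201, 0.255, 0.315. This does not depend on whether the rates are read as 24- or 30-month rates.

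**3. Reproducing the table.** Split the 24 months into short intervals. In each, let D be the expected events, p0 the treatment arm's share of those at risk, and p1 its expected share of events. Then

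power = Φ{ ( |Σ D(p1 - p0)| - 1.96 √[Σ D p0(1 - p0)] ) / √[Σ D p1(1 - p1)] }.

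Example, 80 per arm, rate 0.042: the sums are 5.175, 3.805 and 2.221, so power = Φ[(5.175 - 1.96 × 1.951)/1.490] = Φ(0.91) = 0.818.

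| Per arm | Recomputed | Printed |
|---|---|---|
| 50 | 0.571 / 0.474 / 0.386 | 0.57 / 0.47 / 0.38 |
| 80 | 0.818 / 0.709 / 0.592 | 0.82 / 0.71 / 0.59 |
| 100 | 0.906 / 0.815 / 0.700 | 0.91 / 0.82 / 0.70 |

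All nine cells agree within 0.006. Expected events at 80 per arm are 15.2, 16.0 and 16.7. With so few events the formula is slightly optimistic in the first column: simulated log-rank tests (20,000 per cell) give 0.793/0.702/0.593 at 80 per arm and 0.877/0.796/0.697 at 100.

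**4. The stated hazards do not produce the table.** Hazards of 1.00 and 0.50 in the same formula give 0.848, 0.965 and 0.988 at 50, 80 and 100 per arm, with about 120 events at 80 per arm. No column looks like this.

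**5. Attrition.** The plan says follow-up ends when the event occurs, "or (b) they drop out of the study, or (c) the study ends and the patient is censored while still being actively followed". Dropouts therefore contribute time until censoring. With 100 per arm and 20% exponential attrition, power is 0.867/0.766/0.648, so still only one column exceeds 0.80.

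**6. Sensitivity: hazard ratio 0.50 at the table's control rate.** The plan does not state this pairing. It is computed because the documents give no control rate for the composite. Ranges run from the formula above to the Schoenfeld approximation.

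| Scenario | Expected events | Power |
|---|---|---|
| 80 per arm | 19 | 0.30–0.33 |
| 100 per arm, 20% attrition | 21 | 0.33–0.36 |
| 100 per arm, no attrition | 24 | 0.37–0.39 |

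Reading 0.192 as a 24-month rate raises these to at most 0.39 at 80 per arm and 0.47 at 100. Power of 0.80 for a hazard ratio of 0.50 needs 4 × (1.96 + 0.84)² / (ln 2)² ≈ 66 events, or 66/160 = 41% of completers. At the table's control rate, 0.80 power instead requires a hazard ratio of 0.21 (80 per arm), 0.24 (100 per arm with attrition) or 0.26 (100 per arm).

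**The case against.** The strongest reply is that the text corrects itself. The paragraph immediately before the table names the published rates as its source, and the columns carry those rates as headings. A careful reader would see that the table is not for a hazard ratio of 0.50 and would treat the earlier paragraph as a leftover. That lowers the risk of misreading, but the plan still states a power basis for which it shows no power.

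Three further points have some force.

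- The plan sets no target power, so 0.80 is an outside benchmark. In the 100-per-group row, which matches the number randomised, two of three columns pass it. But the plan itself argues from 160 completers, and crediting dropouts with their censored time leaves one column above 0.80.
- The scenario in step 6 joins one paragraph's hazard ratio to the other's control rate. That is a fair caveat: the composite could have a higher event rate than the source's mortality, and power would then rise. If everyone were followed to a common close after the 50-month accrual and 24 further months, power for a hazard ratio of 0.50 would be about 0.55 to 0.63 at 80 per arm and 0.64 to 0.72 at 100. The plan, however, describes a 24-month study.
- The conclusion on sufficiency is worded for the study as a whole and repeats the primary-endpoint conclusion. This is true, but it stands directly beneath the event table with no qualification.

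The endpoint is secondary, and the study has been in data analysis only since January 2017 (section 7.4). This limits the consequences to documentation and interpretation.

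**Conclusion.** The concern holds. The event-power text and table rest on incompatible assumptions: hazard ratio 0.50 against 0.20 to 0.32, control hazard 1.00 against 0.085 per year, and about 120 expected events against 15 to 17 at 80 per arm. The table is a valid calculation for its own rates, under a log-rank approximation that is slightly optimistic in the first column. It does not show power for a halving of hazard. Adequate power for clinical events holds only for the most extreme tabulated effect, or under the untabulated hazards of 1.00 and 0.50. For context, section 7.4 cites a "significant reduction (16-21% relative risk reduction) of the risk of clinical cardiovascular events" as the expected benefit; this is not a design assumption and is well short of any tabulated effect.

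The implied hazard ratios assume only constant hazards. The power figures also assume 24 months of follow-up per participant. The figures for a hazard ratio of 0.50 further depend on a control rate that the documents do not give for the composite. The documents do not show which basis was intended. The matter should be fixed, but it concerns the secondary endpoint alone.

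**What to change.** In section 6.0, state one hazard ratio and one 24-month control risk for the composite, and make text and table agree. The choice is the sponsor's.

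- If the table is kept: delete the sentences giving the hazard ratio of 0.50, the hazards of 1.00 and 0.50 and the medians. Label the columns with hazard ratios 0.20, 0.26 and 0.32 and a control hazard of 0.085 per year. Note that the source rates are described as mortality while the endpoint is a composite.
- If a hazard ratio of 0.50 is kept: recompute the table at a stated control risk for the composite, preferably over a range.

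Either way, replace the claim of sufficiency, as it applies to clinical events, with the power actually obtained. Interpret the third aim through the hazard ratio and 95% confidence interval from the Cox model already planned. Leave the primary-endpoint sample-size statement as it is.

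The cost is a few sentences and at most one new table, plus a less favourable power statement for a secondary endpoint. Enrolment, data collection and the planned log-rank and Cox analyses do not change.

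### Event power is stated at an undivided two-sided 5%, but the multiplicity section lists time to events among the outcomes and promises a correction without defining its family, divisor or exemptions

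*Combined protocol and SAP*

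**What the plan says.** Four statements bear on the significance level.

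- **Primary power (6.0 Statistical Section).** The wall-volume comparison is sized at an undivided level: "The table below shows the power to detect this difference at the 5% level of significance, assuming 80 subjects in each group". Sidedness is not stated.
- **Event power (6.0, secondary endpoint).** "Using a twosided test at the 5% level of significance, we obtained the following results". At 80 per group the table prints 0.82, 0.71 and 0.59. The text then concludes that recruiting 200, with 160 completing, is enough.
- **Multiplicity (6.0, Data Analysis, item 2).** The item opens with "we will evaluate multiple outcome measures: changes in plaque architecture and composition measured by MRI, and time to events". It commits to three approaches together: (i) naming a primary outcome, (ii) a correction, worded as "ii) correcting for multiple testing, such as Bonferroni adjustment", and (iii) a combined event endpoint.
- **Endpoints (1.1 Study Objectives).** One primary efficacy endpoint is named, internal carotid wall volume, followed by secondary endpoints A to E. The combined clinical events are C, and scan reproducibility is E.

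Item 2 does not say which tests form the corrected family, how many there are, which method is final, or whether any test is exempt. Item 3, which describes the analysis of each hypothesis, gives no significance level.

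**The concern.** The event test is one of the outcomes for which item 2 promises a correction, yet its power was calculated as if no correction existed. Both statements cannot describe the same test. Either the event comparison is outside the corrected family, which the plan does not say, or the printed powers do not apply to the test that will be run.

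Two things depend on this. One is how an event p-value between the corrected and uncorrected thresholds is read. With the family and method unwritten, that choice could be made after the results are known, in a trial whose treatment is open-label. The other is the claim that 200 participants are sufficient, which the plan repeats directly below the event power table.

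**Working it through.** **Step 1. Which level underlies the primary table?**

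Inputs, all from section 6.0: "the standard deviation of the differences between 18 months and baseline was 125 mm³"; "The baseline mean for the entire group was 300.0"; "finding a 40% decrease in plaque volume in the image-guided arm compared to a 20% decrease in the conventional treatment arm"; 80 per group in equal allocation ("These calculations were based on the optimal allocation of equal numbers to the two arms").

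- Design difference: (0.40 − 0.20) × 300 = 60 mm³.
- Standard error: 125 × √(2/80) = 19.76 mm³.
- Noncentrality: 60 / 19.76 = 3.04, with 158 degrees of freedom.
- Power = P(|T| > t at 1 − α/2), T noncentral t.

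| Difference (mm³) | Plan | Two-sided 0.05 |
|---|---|---|
| 30 | 0.33 | 0.33 |
| 45 | 0.62 | 0.62 |
| 60 | 0.85 | 0.855 |
| 75 | 0.96 | 0.965 |
| 90 | 0.99 | 0.995 |

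The table is an undivided two-sided 5% calculation. A one-sided 5% test would give 0.92 for 60 mm³. The recruitment figure also reproduces: 160 / 0.8 = 200.

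If the primary were itself corrected by Bonferroni, power for 60 mm³ would be 0.78 at 0.025 (two tests), 0.73 at 0.0167 (three) and 0.69 at 0.0125 (four). Observed differences between 39.0 and 44.7 mm³ would pass at 0.05 but fail at 0.025. Under the design effect that zone holds 0.855 − 0.779 = 7.6% of trials.

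**Step 2. Reproduce the event table.**

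Inputs from section 6.0: control rate 10/52 = 0.192; treatment rates 2/48 = 0.042, 5/94 = 0.053 and 3/46 = 0.065; two-sided 5%. Rates are taken as printed.

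No single log-rank formula tried matches the whole table. Freedman's form uses E = n(pc + pt), θ = ln(1 − pt)/ln(1 − pc) and power = Φ(√E·|1 − θ|/(1 + θ) − z). At 80 per group it gives 0.82, 0.75 and 0.66, which is 4 and 7 points above print in the last two scenarios. Fisher's exact test comes closest to the 80-per-group row:

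| n per group | Plan | Fisher exact, 0.05 |
|---|---|---|
| 50 | 0.57 / 0.47 / 0.38 | 0.54 / 0.44 / 0.35 |
| 80 | 0.82 / 0.71 / 0.59 | 0.83 / 0.73 / 0.61 |
| 100 | 0.91 / 0.82 / 0.70 | 0.91 / 0.83 / 0.72 |

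It serves here only as a calibrated stand-in for the planned log-rank test.

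**Step 3. Apply a correction to the event test, 80 per group, Fisher exact.**

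| Tests assumed | Alpha | Power at 0.042 / 0.053 / 0.065 |
|---|---|---|
| 1 (none) | 0.05 | 0.83 / 0.73 / 0.61 |
| 2 | 0.025 | 0.73 / 0.61 / 0.49 |
| 3 | 0.0167 | 0.67 / 0.55 / 0.42 |
| 4 | 0.0125 | 0.62 / 0.49 / 0.37 |

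For two tests the loss is 0.826 − 0.729 = 0.097, 0.726 − 0.611 = 0.115 and 0.611 − 0.490 = 0.121, so 10 to 12 points. Freedman's form at 0.025 gives 0.74, 0.65 and 0.55, a loss of 8 to 11 points. The loss is therefore similar under both methods, although Freedman's starting point does not match the plan.

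**The case against.** The strongest reply concerns the primary. A reader might infer that the plan gives the primary test two incompatible levels, so that a p-value of 0.03 is positive by the power section and negative by item 2. The documents do not support that. Item 2 begins with naming a primary outcome, which is itself a multiplicity device and would achieve little if the primary were then corrected along with everything else. Section 1.1 names one primary endpoint, and section 6.0 sizes it at 5%. The ordinary reading is that the primary keeps 5% and the other outcomes are corrected. Some doubt remains, because item 2 does not say so and section 1.2 speaks of primary endpoints in the plural, covering plaque volume and composition. That makes it an ambiguity worth closing, no more.

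Three further replies have weight.

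- Bonferroni is offered only as an example and the number of tests is not given, so the size of the power loss is conditional. This stands, and the figures above are a range under assumptions.
- The claim that 200 participants suffice for events was weak before any correction, since two of the three printed powers at 80 per group are below 0.80. This also stands. Multiplicity worsens that weakness but does not create it.
- Section 7.4 records the study as being in data analysis only since January 2017, so restated planning power cannot alter recruitment. True, but the decision rule for the event test and the description of its power still matter to the report.

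None of these replies removes the mismatch for the event test, which item 2 names and the power table leaves uncorrected.

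**Conclusion.** The point holds for the event endpoint. Its power is stated at an undivided two-sided 5%, while the plan commits to a multiplicity correction over outcomes that include it. If the correction applies, the printed powers at 80 per group are overstated by about 10 to 12 points for two tests and by more for a larger family. This rests on an assumed number of tests, on a Bonferroni-type split, and on Fisher's exact test as a stand-in that comes within about 2 points of the printed row.

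For the primary endpoint the plan is unclear but not contradictory. The 0.85 is correct at the level on which it was computed, and 0.78 would follow only from a literal reading that corrects the primary over two tests.

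**What to change.** In section 6.0, Data Analysis, item 2:

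1. State that the single primary contrast, the 24-month change in carotid wall volume, is exempt from correction across endpoints and is tested at an overall two-sided 5%. Make this subject to any alpha allocation for the two interim efficacy analyses in section 7.6, for which none is stated.
2. Replace the open-ended Bonferroni example with Holm's procedure, which is never less powerful than Bonferroni, applied to a listed family of between-arm secondary tests. Leave out the reproducibility endpoint, which is analysed by weighted kappa, ICC and Bland-Altman plots and is not a between-arm test.

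In the event power text:

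3. Label the table as unadjusted, or recompute it at the first-step Holm level, 0.05 divided by the number of listed secondary tests. Describe that figure as conservative, because Holm's later thresholds are larger.
4. Limit the statement that 200 participants are sufficient to the primary endpoint.

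The cost is a few sentences and one relabelled or recomputed table, with no added participants. The downside is a less favourable stated event power.
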